Study Design:	
This is a multi-center, single-arm, quantitative study evaluating the effectiveness of the TatchSleep Pro wireless sensors as a tool to aid in sleep apnea diagnosis as compared to an overnight PSG evaluation.
 
Investigators will identify approximately 50 eligible patients who have been recommended to receive an overnight PSG for the detection/evaluation of sleep apnea. After informed consent is obtained, a brief sleep-related medical history will be collected including relevant demographics. Females of childbearing potential will be asked to undergo a urine dipstick pregnancy test to determine their eligibility for inclusion in the study.
 
Patients will undergo their PSG test while simultaneously wearing 2 TatchSleep Pro patches and an FDA-cleared pulse oximeter compatible with and connected to the TatchSleep Pro system for a single night at the clinic. The same make and model of pulse oximeter will be used for all subjects. Patients will be observed overnight by trained sleep technicians who will setup the TatchSleep Pro device and collect the sleep data via the companion smartphone application.
 
A follow-up communication will be made with patients within 5 days after the sleep study to assess any adverse events.
 
Following the data collection, sleep data from PSG and TatchSleep Pro will be scored by an independent qualified sleep technologist (the primary reader) to yield an analysis of the accuracy of TatchSleep Pro compared with the PSG signals. At least one and up to two additional readers (secondary readers) will score only the TatchSleep Pro data to obtain an estimate of inter-rater reliability.

Study Device:	TatchSleep Pro paired with the same make and model of compatible FDA cleared pulse oximeter for all subjects
Eligibility Criteria:	
Inclusion Criteria:
 
 1. Be at least 21 years of age.

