8.7 Onsite PSG Study Scoring and Export

After the completion of data collection from patients, de-identified PSG signals will be exported from the PSG at the clinical site including, at a minimum, manual position annotations and sleep staging scored according to the standard of care by a sleep technologist at the study site. Raw PSG sleep data (including, at a minimum, respiratory effort, respiratory pressure, respiratory flow and oxygen saturation signals) will be extracted and presented to qualified readers as described below.

9. Study Scoring

Once study enrollment and all sleep tests are complete, and all exported PSG data (with position annotations and sleep staging) has been received by the Sponsor, the primary reader will score all sleep study recordings made simultaneously with TatchSleep Pro and the PSG device from all sites. The primary reader will be blinded to the device used to collect the data under review as well as any information which may allow them to link the two studies from each patient. The AHI will be calculated for each study, and the set of AHIs derived from TatchSleep Pro data will be compared with those derived from PSG data using Pearson correlation to demonstrate accuracy (see Protocol Section 11 for more details). At least one and up to two additional readers (secondary readers) will each score all sleep study recordings made using the TatchSleep Pro device at all sites. The AHIs derived from these scorings will be used to calculate the inter-rater reliability for the TatchSleep Pro device signals.

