9.3 Blinding

All studies will be presented on the same viewing and scoring platform. The readers will be blinded to patient identification and the data collection device for each study. Specifically:

- All data presented to the reader will be fully anonymized and will not include any information which could allow the reader to link a subject's two data sets. All Protected Health Information (PHI), ID numbers, and study meta-data such as time

and date will be removed.

- The reader will review patient studies in a predetermined randomized order such that sequential readings of data from the same patient will be avoided.
- All studies will be reviewed using the same analysis software, and using identical, system-agnostic signal labeling (eg, "Flow" will be used to label both the TatchSleep Pro TATCH-SUM-FLOW and the PSG Airflow waveforms).

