9.5 AHI Calculation

The AHI will be calculated for each study following scoring. The PSG total sleep time (with device-specific total artifact time subtracted) will be used as the AHI denominator.

10. Reader Selection

Sleep technologists of any age, sex, race, ethnicity, or institutional affiliation who are qualified to read PSG night tests may participate as study readers. The selected readers must meet the following criteria:

- Be Registered Polysomnographic Technologist (RPSGT) or Registered Sleep Technologist (RST) certified
- Currently participant in the American Academy of Sleep Medicine Inter-Scorer Reliability (AASM ISR) program
- Be experienced in reading PSG night tests using at least one commercially available analysis software package
- Have provided a current curriculum vitae (CV)
- Have provided a signed Readers' Agreement

The qualified and confirmed readers will complete a training program on the analysis software to be used for the study, as well as on the study protocol prior to their participation in this study.

11. TatchSleep Pro Materials and Management

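### Section 9.3 promises device blinding for every reader, but protocol training under Section 10 tells a secondary reader who knows their role that every file is TatchSleep Pro

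*Combined protocol and SAP*

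**What the plan says.** - **Blinding (Section 9.3).** "The readers will be blinded to patient identification and the data collection device for each study". The statement covers readers in general and makes no exception. The means are anonymised files, removed metadata, a randomised reading order and neutral channel labels.
- **Training (Section 10).** Before taking part, the qualified readers "will complete a training program on the analysis software to be used for the study, as well as on the study protocol". Primary and secondary readers are not distinguished, and no part of the protocol is held back.
- **Secondary readers' files.** The synopsis (Study Design) says: "At least one and up to two additional readers (secondary readers) will score only the TatchSleep Pro data". Section 9 says that they "will each score all sleep study recordings made using the TatchSleep Pro device at all sites".
- **Primary reader's files (Section 9).** "the primary reader will score all sleep study recordings made simultaneously with TatchSleep Pro and the PSG device from all sites", and "The primary reader will be blinded to the device used to collect the data under review".
- **Use of the secondary scorings (Section 9).** "The AHIs derived from these scorings will be used to calculate the inter-rater reliability for the TatchSleep Pro device signals". Section 14.6 names the ICC with a 95% confidence interval. It gives neither the form of the ICC nor the readers who enter it.

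**The concern.** The safeguards in 9.3 hide the device only from someone who could be looking at either system. They work for the primary reader, whose files are a mix. They hide nothing from a reader who knows that the whole set comes from one system.

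At stake is the interpretation of the inter-rater ICC, a secondary endpoint that serves the reader-reliability objective in Section 3.2. Readers mark events and also mark artifact and movement at their discretion. Under 9.2 and 9.5 those marks change the AHI denominator. Knowing that a file comes from the investigational device could therefore alter both the event count and the denominator. If one reader in the ICC is blinded and another is not, any such change is counted as reader disagreement. The study report would also describe all readers as device-blinded, and Section 15.5 foresees use of the analysis in regulatory submissions.

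**Working it through.** **Step 1. Does the blinding claim hold for a secondary reader?**

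| | Primary reader | Secondary reader |
|---|---|---|
| Files (Section 9; about 50 patients) | Both systems, about 100 | TatchSleep Pro only, about 50 |
| Trained on the protocol (Section 10) | Yes | Yes |
| Can deduce the device of a given file from the protocol | No | Yes, if they know their role |

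No section conceals roles, limits the training, or adds PSG files to the secondary set. Even an unannounced role could be inferred by someone who has read the protocol and receives about 50 files instead of about 100.

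**Step 2. Which readers enter the ICC?** With one secondary reader, an ICC needs the primary reader's scores as its second set. With two, it could be computed from the secondary readers alone or from all three. Section 14.8 gives one indirect clue: a 95% margin of error of 5% for 46 subjects at an ICC of 0.95. To reproduce it, use the F-based interval for a one-way ICC:

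- F0 = (1 + (k−1)ρ)/(1−ρ), with df1 = n−1 and df2 = n(k−1).
- F_L = F0/F(0.975; df1, df2) and F_U = F0 × F(0.975; df2, df1).
- Each limit is (F−1)/(F+k−1).

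Results for n = 46 and ρ = 0.95:

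- k = 3: F0 = 2.90/0.05 = 58; interval 0.920 to 0.970; full width 0.0499.
- k = 2: F0 = 1.95/0.05 = 39; interval 0.912 to 0.972; full width 0.060.

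The 5% therefore matches the full width for three readers. It does not match a half-width: the large-sample half-widths are 0.024 (k = 3) and 0.028 (k = 2). Three readers fits the primary reader plus two secondary readers, but this suggests the composition and does not prove it.

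**Step 3. How large could an effect be?** The documents cannot answer this. The figures below are illustrations for two readers and an ICC of 0.95 without the effect. The 0.95 comes from 14.8, where it is a PSG-versus-TatchSleep value in 19 subjects and not a between-reader value. The between-subject AHI SD, S, is assumed to be 10 to 20. Error variance is v = S² × 0.05/0.95.

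*Additive shift b in the unblinded reader, absolute-agreement form:* ICC = S²/(S² + v + b²/2). For b = 3 and S = 10: 100/(100 + 5.263 + 4.5) = 0.911. For b = 3 and S = 20: 400/(400 + 21.053 + 4.5) = 0.940.

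| Shift (events/hour) | S = 10 | S = 20 |
|---|---|---|
| 1 | 0.946 | 0.949 |
| 2 | 0.932 | 0.946 |
| 3 | 0.911 | 0.940 |
| 5 | 0.849 | 0.923 |

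A consistency-form ICC stays at 0.95 under a pure additive shift.

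*Proportional change, factor f, with mean AHI m assumed equal to S:* ICC = 2fS²/[(S² + v)(1 + f²) + ((1−f)m)²]. For f = 0.90, with S = 1: 1.8/(1.0526 × 1.81 + 0.01) = 0.940. For f = 0.85 the result is 0.926, and for f = 0.80 it is 0.906. The consistency form drops the last term in the denominator and gives 0.945 at f = 0.90 and 0.927 at f = 0.80.

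*Change in the unblinded reader's error variance only:* ICC = 1/(1 + 0.0526 × average multiplier). Doubling gives 1/(1 + 0.0526 × 1.5) = 0.927. Halving gives 1/(1 + 0.0526 × 0.75) = 0.962. The direction is therefore open as well.

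**The case against.** Four arguments carry weight.

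1. **Roles may not be disclosed.** A reader might infer that the blinding of secondary readers is bound to fail. The documents do not go that far. They never say that readers are told their role, and Section 10 does not describe how much of the protocol the training covers. This stands, so the conclusion is conditional on the reader knowing their role. But nothing in the plan conceals the role either, and 9.3 makes its promise without any measure suited to a single-device set.

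2. **The ICC may not mix blinded and unblinded readers.** In Section 9 the sentence on reliability follows directly on the secondary readers' scorings, so with two of them the ICC could be secondary versus secondary. Both would then hold the same knowledge. This also stands: mixing is forced only with a single secondary reader, or if the primary reader's scores are included. Section 14.6 leaves the matter open.

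3. **Little hangs on it.** Inter-rater reliability is estimated without a hypothesis or a success threshold. Success rests on the three null hypotheses in 14.5, which compare PSG with TatchSleep Pro AHI. The primary reader scores both systems for that comparison and is separately blinded in Section 9. This stands and limits the importance of the point.

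4. **Modest effects are small beside the stated precision.** In the proportional illustration, a 10% change moves the ICC by 0.01, against a stated 5% margin. That is fair, but the shift is assumed in either direction of argument, and larger shifts are not excluded.

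A further inference is tempting: that protocol training compromises the primary reader too, because it reveals the paired recordings, the endpoint and the performance goals. The documents do not support this. Such knowledge does not show which files are paired or which system produced a given file, and the measures in 9.3 address exactly that.

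**Conclusion.** The plan states a blinding property that it does not secure for the secondary readers. The conflict between 9.3, Section 10 and the file allocation in the synopsis and Section 9 is real. It takes effect when a secondary reader knows their role. It reaches the ICC only when the primary reader's TatchSleep Pro scores are part of it.

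Size and direction are unknown. The illustrative shifts of 1 to 5 events/hour give ICCs from 0.949 down to 0.849, and they rest on an assumed AHI SD of 10 to 20, two readers, an absolute-agreement form and a starting value of 0.95. Other assumptions leave the ICC unchanged or raise it. Only an estimation-only secondary endpoint and the wording of the blinding claim are touched. The co-primary correlation and limits of agreement are not affected. The point is worth correcting because the correction is cheap, not because the trial's conclusion depends on it.

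**What to change.** **Preferred.** In Section 10, replace training on the protocol with training on the software and a reader scoring manual. The manual holds the content of 9.2 and 9.4 with neutral labels. It does not disclose reader roles or which system's files each reader receives. Readers should not be told the expected number of files. The Readers' Agreement should observe the same limits.

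**If that is not possible, or readers have already seen the protocol:**
- limit the device-blinding claim in 9.3 to the primary reader;
- state in 14.6 which readers enter the ICC;
- if two secondary readers are used, report the primary–secondary and secondary–secondary ICCs separately. With one secondary reader only the first exists, and it should be labelled as a comparison of a device-blinded reader with one who is not.

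**Cost.** One changed sentence in Section 10 and a short manual that the sponsor must write and keep under version control. The fallback costs a few sentences in 9.3 and 14.6. Neither needs extra patients, readers or readings.

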11.1 TatchSleep Pro Description

TatchSleep Pro is a system comprised of wearable and wireless sensors designed to collect physiological parameters related to sleep disorders in patients. The system has two sensor patches and makes use of a compatible FDA-cleared pulse oximeter. Each patch consists of a wearable sensor and a bottom layer of double coat medical-grade adhesive. This adhesive is safe for patient use and enables the patch to stay affixed to the body (thorax and abdomen) throughout the night. The sensor also connects directly to a battery which is hidden within the patch. During the study, patients will be asked to wear all three sensors (one patch on the abdomen, one patch on the thorax and the pulse oximeter on a finger). Data from the patches and pulse oximeter are transmitted wirelessly throughout the night to a secure cloud server via the companion mobile application for clinicians to upload to a sleep analysis platform.

11.2 Shipping, Storage and Accountability

TatchSleep Pro sensors will be sent in packages to the clinical site by a tracked postal service prior to the enrollment of the patients. Each shipment will include up to 10 patient kits, depending on the site projected enrollment rate. Each TatchSleep Pro kit will contain 2 patches, a pulse oximeter, and a User Manual. Smartphones will be provided to the clinical site with the TatchSleep Pro companion application pre-loaded. Study staff will be trained on the use and functionalities of TatchSleep Pro and the companion application prior to enrollment.

TatchSleep Pro kits will be stored at room temperature at the clinical site in a secured, limited access location, under the supervision of the Investigator or designee.

The Investigator or designee will be responsible for taking an inventory of each shipment of TatchSleep Pro kits received and comparing it with the accompanying shipping invoice to confirm accuracy of the shipment and its contents. All used and unused TatchSleep Pro wearable sensors will be retained at the site. After full device accountability and reconciliation, the Investigator will return the used and unused kits to the Sponsor or its designee. Disposition and use of all TatchSleep Pro sensors should be documented, including any that are lost or damaged.

11.3 TatchSleep Pro Associated Risks

Per the FDA guidelines "Significant Risk and Nonsignificant Risk Medical Device Studies" [4] and based on 21 CFR 812.3(m), TatchSleep Pro qualifies as a Non-Significant Risk device since TatchSleep Pro:

- **Is not** intended as an implant and **does not** present a potential for serious risk to the health, safety, or welfare of a subject;
- **Is not** purported or represented to be for use supporting or sustaining human life and **does not** present a potential for serious risk to the health, safety, or welfare of a subject;
- **Is not** for a use of substantial importance in diagnosing, curing, mitigating, or treating disease, or otherwise preventing impairment of human health and **does not** present a potential for serious risk to the health, safety, or welfare of a subject; or
- **Does not** otherwise present a potential for serious risk to the health, safety, or welfare of a subject.

Although there is minimal risk in using the TatchSleep Pro technology, patients may experience some slight discomfort wearing the TatchSleep Pro patches or the compatible pulse oximeter throughout the night. It is possible that patients with sensitive skin may experience mild skin irritation due to the patch adhesive. A similar skin irritation risk exists in the PSG test. Patients will be clearly instructed that they are allowed to remove the TatchSleep Pro patches, pulse oximeter, or the adhesive from the PSG study if they experience skin irritation or significant discomfort at any point. A previous analysis showed no adverse events amongst a cohort of 19 patients undergoing full night tests wearing the TatchSleep Pro patches.

There is also a risk that the technology will not function as anticipated causing partial recording of the study night which might make data unusable. It will be explained to the participants that these technologies are still evolving, and they may experience glitches or malfunctions during the study.

12. Adverse Events

12.1 Adverse Event Definition

An adverse event (AE) is any symptom, sign, illness or experience that develops or worsens in severity during the course of the study. Intercurrent illnesses or injuries should be regarded as adverse events. Abnormal results of diagnostic procedures are considered to be adverse events if the abnormality:

- results in study withdrawal
- is associated with a serious adverse event
- is associated with clinical signs or symptoms
- leads to additional treatment or to further diagnostic tests
- is considered by the investigator to be of clinical significance

An adverse device effect (ADE) is any reported AE that is considered device-related.

12.2 Severity

Adverse events will be classified by the investigator as mild, moderate, severe, life threatening, or fatal.

When the severity of the AE increases over time, the change in severity will be recorded in the source documents as a new AE and the original AE will stop when the new AE starts. The Principal Investigator or the delegated person must record all AEs that occur during the study from the time of TatchSleep Pro placement until study completion or Early Termination, regardless of their relationship to study device or procedure.

The Principal Investigator will evaluate the severity of AEs and determine their relationship to the study device or procedures. Any action or procedure followed by the patient or clinical staff to alleviate the AE will be documented regardless of who recommended such action or procedure. The clinical course of each event will be followed until resolution, stabilization, or clinically significant improvement that requires no further follow-ups in the opinion of the Investigator.

12.3 Serious Adverse Events (SAE) and Unanticipated Adverse Device Effect (UADE)

A serious adverse event (SAE) may or may not be considered related to the device and may be described as follows:

- Death due to any cause
- Life-threatening condition
- Persistent or significant disability/incapacity
- Any event resulting in hospitalization or prolonged hospitalization
- Congenital abnormality
- Is considered an important medical event by the Investigator or Sponsor

A UADE is any serious adverse effect on health or safety, or any life-threatening problem or death caused by, or associated with, a device, if that effect, problem, or death was not previously identified in nature, severity, or degree of incidence in the investigational plan or application (including a supplementary plan or application), or any other unanticipated

serious problem associated with a device that relates to the rights, safety, or welfare of subjects.

12.4 Event Reporting

All AEs will be recorded on the CRF by the Investigator or designee regardless of their relationship to the study device. SAEs and ADEs should be reported to the Sponsor within 24 hours of knowledge of the event using the SAE/ADE Report Form provided by the Sponsor. UADEs must be reported by the clinical investigator to the sponsor and the reviewing IRB, no event later than 10 working days after the investigator first learns of the event. Sponsors must immediately conduct an evaluation of a UADE and must report the results of the evaluation to FDA, all reviewing IRBs, and participating investigators within 10 working days after the sponsor first receives notice of the effect.

13. Early Termination

Study patients may decide to withdraw from the research study without any penalty and for any reason. Study patients may be considered withdrawn if they state an intention to withdraw or fail to participate. Although patients are not required to provide a reason for withdrawal, they will be asked by research staff about their decision. The Investigator also reserves the right to remove a study participant from the study at any time for any reason (e.g. non-compliance with study requirements, safety reasons).

Study patients may also withdraw permission for the use and disclosure of any of their protected information for research but must do so in writing to the Principal Investigator.

14. Data Analysis

14.1 General Considerations

Summary statistics for continuous variables will include the mean, standard deviation, median, and range. Categorical variables will be presented as counts and percentages. All confidence intervals provided will be calculated at the 95% confidence level, unless otherwise noted. All null hypotheses will be tested against two-sided alternatives at the 5% significance level, unless otherwise noted. Any other details not included in this protocol will be included in the Statistical Analysis Plan.

